Summary. There is renewed interest in determining whether cognitive retraining directed to enhancing performance on underlying component processes may improve the effectiveness of treatment for SUDs. Current studies offer promise and suggest directions for additional research. This project is designed to address two areas of clinical and scientific relevance; the systematic inclusion of women and the extension of training paradigms to consider transfer of gains to tasks engaging emotion processing. Additionally, given the limited data on longer-term effects, we will extend the follow-up to cover the first 90 days following discharge, i.e., through a known period of heightened vulnerability [79].

Overall Summary. Neurobehavioral deficits are common in treatment-seeking persons with AUDs. Cognitive training directed to commonly compromised processes shows promise and merits further research. As a pilot project, the scope of work is necessarily limited. In this application, we seek to extend current work by examining sex differences in response to cognitive training in attention/working memory and by investigating whether training engaging emotion processes differentially affects outcomes, and if the sexes differ in their response to this training. We will also examine relationships among demographic variables, comorbid substance use, performance gains, and post-treatment outcomes (i.e., over a 3 month period), thereby providing direction for consideration of individual differences in training outcomes. Together these data will inform questions of feasibility, identify potential subgroups (beyond sex) varying in response, and guide the development of a more comprehensive R01 application assessing cognitive training among treatment-seekers with AUDs.

5. Aims (H=hypothesis, E=empirical question)

Aim 1: Investigate potential sex differences in response to cognitive training. In the absence of a consistent literature, we ask: **E1:** Will men and women show differential transfer of gains in post-intervention testing? **E2:** Will transfer of gains for men vs. women differ on the basis of transfer task demands? **E3**: Will they differ in the degree to which they demonstrate improvement across training? **E4**: Will the relationship between baseline performance, training gains, relapse and/or post-treatment adaptation differ for women and men?

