Aim 2: Determine whether stimulus characteristics (neutral vs. affective) define transferability of gains and/or training trajectories. Given current literature, we predict that; **H1**: Active training, regardless of condition, will produce greater performance gains than the control condition, **H2**: Training with affective stimuli as opposed to neutral stimuli will differentially benefit performance on transfer tasks engaging affective stimuli, and, **H3**: Training gains will be more readily transferred to tasks engaging highly similar cognitive demands (processes) vs. more general processes. We ask, **E5**: To what extent do training trajectories vary as a function of training stimulus characteristics?

Aim 3: Explore sex by training condition interactions. Existing studies suggest that: **H4**: Training with affective stimuli may differentially benefit women as compared to men, although we expect that both sexes are likely to show transfer of gains within the affective condition (**H5**). We ask, **E6**: Do training trajectories vary by sex? **E7**: Are training trajectories subject to the sex by condition interaction?

Secondary/Exploratory Aims: The study provides the opportunity to examine relationships between/among a variety of individual characteristics beyond those treated as key covariates, e.g., age, education, alcohol use history, that may impact the efficacy of training interventions, e.g., pre-treatment levels of functional adaptation, mood/affect during treatment, and comorbid substance use. These associations will be examined in exploratory analyses relying on correlational methods and will inform future projects. Similarly, Ss acceptability of the intervention will be assessed through preliminary methods and will be considered in structuring future interventions.

6. Research Plan

The primary design is a 2 (Sex) by 3 (Training Condition: Neutral, Affective, Control) by 2 (Time: Baseline, Post-training) mixed design. The control Ss will meet identical selection criteria but complete only baseline and retesting, controlling for abstinence-related improvement. R03 limitations prohibit the inclusion of an active control condition [56]. Follow-up phone interviews allow preliminary assessment of the impact of cognitive training on post-treatment functioning. Cell sizes (Table 1) were informed by power analyses and

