the constraints of the R03 mechanism [see Data Analysis]. Assignment to neutral vs. affective training group will be randomized within sex. To minimize confounds associated with conducting active interventions and control conditions concurrently within the facilities (i.e., Ss being unwilling to serve as controls due to differential compensation), ~ half of the control Ss will complete participation at the initiation of the project and ~half after training groups have been recruited. Further, separate ICFs are utilized, with control ICFs remaining unlabeled (i.e., not referred to as a "control" group).

Condition:	Sex:		
	Men	Women	Total
Neutral	15	15	30
Affective	15	15	30
Control	15	15	30
Table 1: Overall Study Design			90

The overall structure of the intervention involves baseline cognitive assessment including performance on the standard and emotional Stroop, 3 weeks of training on neutral or emotional versions of two tasks with strong demands on attention/working memory (specifically the capacity to suppress response to irrelevancy) and retesting on the cognitive battery and the emotional and standard Stroop. The primary dependent variables are differences between pre- and post-intervention performance on the two Stroop tasks as a function of training condition (including neutral, affective and control), sex, and their interaction. Ss complete a neurocognitive battery at baseline, affording an additional test of improvement and transfer of gains through re-administration after training.

Participant (Ss) Selection Criteria. Ss are recruited from treatment facilities in north central FL with expected length of stays extending across the intervention period. Ss range in age from 25-65 with a minimum of 10 years of education. Ss may not have medical or psychiatric histories which would confound participation or data interpretation, e.g., epilepsy, stroke, untreated hypertension, psychotic disorders, anxiolytic medications, etc. Endorsement of suicidal intent is exclusionary, and is reported to facility clinical staff. Comorbid substance use including nicotine use is not exclusionary and is addressed using both categorical and continuous measures. Ss are not selected by race/ethnicity (~69% Caucasian, 28% African American;7% Hispanic).

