Data Analysis Strategy. General considerations: Statistical analyses will apply SAS Version 9.4 (SAS Institute). Data will be examined for completeness, outliers, and distributional fit with transformations employed, as appropriate. Descriptive statistics, graphical methods and correlational matrices will be used to characterize the data. To examine outcomes over time generalized linear mixed models (GLMM) and linear contrasts will be used. Dependent variables are noted in task descriptions. Aims 1-3 are addressed in both transfer and training analyses, *Feasibility*: The design should minimize dropout, however we will evaluate dropout rates and the number of trainings completed prior to dropout as a function of sex, training condition, and the interaction. For selected analyses, missing data techniques will be employed; pattern-mixture models based on point of loss and sensitivity analysis will aid in interpretation. Transfer effects: GLMM analyses will be employed to examine effects of training condition, sex, and their interaction on transfer task performance. Dependent variables include RT, ACC, and efficiency (ACC/RT) for each Stroop condition (congruent, incongruent, neutral) and the cognitive battery. Training Effects: Linear contrasts will be utilized to compare performance on the training tasks across training session, group, and sex. We will explore whether the two training tasks are differentially related to transfer of gains. Secondary aim: Exploratory methods will be applied to a) examine associations between/among measures of functional adaptation, mood/affect, transfer gains and post-treatment substance use, and b) explore potential subgroups/subtypes that vary in response to training and/or post-treatment outcomes. Training session ratings of acceptability and perceived improvement will be compiled to provide proxy indicators of engagement to inform training session development. Power: Schweizer et al. [60], report large transfer effects (Cohen's f's, .82-1.10) but do not address sex differences. Given the developmental nature of the investigation and the intent to identify preliminary data regarding sex differences meriting further study, we will consider sex main effects at $\alpha = .10$. With an estimated moderate effect size (Cohen's f=.25) and a correlation between measures of rho=.5, our power to detect sex effects is .78. Our power to detect transfer effects relative to controls is 1.0 with power =.98 to detect more modest between-group training effects (Cohen's f ~.40; α =.05). For the critical interaction of sex and training condition, and estimating a moderate effect, our power is .96 (α = .05, rho = .5). This estimate fails to account for Ss dropout. Absent guiding estimates, we conducted an analysis with a dropout of 10 Ss/ condition and maintained power =.80.

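### The search for who responds to training relies on correlations with pre-post gain, and E4 has no stated model; neither separates response to training from regression to the mean, practice or recovery

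*Combined protocol and SAP*

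**What the plan says.** Section 6 (Research Plan) defines the main outcomes as change scores: "The primary dependent variables are differences between pre- and post-intervention performance on the two Stroop tasks". E4, under Aim 1 in section 5, asks: "Will the relationship between baseline performance, training gains, relapse and/or post-treatment adaptation differ for women and men".

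The Secondary/Exploratory Aims concern individual characteristics that may affect how well training works, such as functional adaptation, mood and comorbid substance use. Of these the plan says: "These associations will be examined in exploratory analyses relying on correlational methods". The Data Analysis Strategy repeats the aim. It lists functional adaptation, mood/affect, transfer gains and post-treatment use for the associations, and adds a plan to "explore potential subgroups/subtypes that vary in response to training and/or post-treatment outcomes". It gives no method or splitting variable for that search.

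The key covariates given as examples are age, education and alcohol use history. Baseline test score is not among them. An untrained group of 30 is tested twice to control for abstinence-related improvement, but no step says that associations with gain will be compared with those seen in that group.

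**The concern.** Within any one arm, gain is the sum of the training effect, retest practice, recovery with abstinence, and the difference between two measurement errors. A characteristic correlated with gain may be related to any of these. Only the first is response to training.

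The sharpest case is a baseline score set against gain on the same test. The error in the baseline score enters the gain with a minus sign, so low scorers appear to gain and high scorers appear to lose, trained or not. A responder subgroup picked by gain is then in large part a low-baseline subgroup.

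Section 4 (Overall Summary) says the data will identify subgroups that vary in response and guide a larger grant application. If those subgroups reflect regression to the mean or recovery, the next trial would be designed around the wrong people.

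**Working it through.** **Inputs.** From the Power paragraph: rho = .5 between measures, f = .25 as a moderate effect, N = 90 in six cells, two time points. Equal SDs at the two times, and all other values of rho and SD ratio, are assumptions.

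**1. The plan's own figure that uses rho.** For the sex by condition interaction it states: "our power is .96 (α = .05, rho = .5". With noncentrality f² x N x m / (1 - rho) = .0625 x 90 x 2 / .5 = 22.5 on 5 and 84 df, power is .962, which agrees. (With 2 numerator df it would be .991.) So rho = .5 acts as the baseline-retest correlation. It is a planning value, not an estimate.

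**2. Baseline against gain on the same test, no training effect.** With k = SD(post)/SD(pre),

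corr(pre, post - pre) = (rho k - 1) / sqrt(1 + k² - 2 rho k),

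which at k = 1 is -sqrt((1 - rho)/2).

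| rho (k = 1) | r |
|---|---|
| .3 | -.59 |
| .5 | -.50 |
| .7 | -.39 |
| .8 | -.32 |

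At rho = .5, r is -.66 at k = .8 and -.33 at k = 1.25.

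In simulated samples with rho = .5, k = 1 and no training effect, this correlation had p < .05 in 50% of samples of 15, 83% of 30, 95% of 45 and 99% of 60.

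For scale, a median split on baseline would give mean gains of (1 - rho) x sqrt(2/pi) = .5 x .798 = +.40 SD in the low half and -.40 SD in the high half, a gap of .80 SD. At rho = .8 the gap is 2 x .2 x .798 = .32 SD. The plan does not schedule such a split.

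**3. A different measure against gain.** For a characteristic correlated c0 with the first score and c1 with the last, corr = (c1 - c0)/sqrt(2 - 2 rho). This is 0 when c0 = c1. At rho = .5 it is -.10 for assumed values .4 and .3, and -.20 for .5 and .3. The same formula covers a Stroop or battery baseline set against gain on a training task.

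**4. E4's sex contrast.** With the same rho and SD ratio in both sexes, the expected difference between the men's and women's correlations is 0. The simulated false-positive rate was 4.7% (15 v 15), 5.1% (30 v 30) and 5.0% (45 v 45). If reliability differs by sex, the 30 v 30 contrast rejects in about 8% of trials at rho .4 v .6 (r = -.55 v -.45) or .5 v .7, and in 17% at .3 v .7.

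**5. The condition interaction.** Under the same null, the baseline x condition term (60 trained v 30 control) rejected in 5.0% of simulated trials.

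**6. Precision of that term.** With standardised scores and rho = .5 the residual SD is sqrt(1 - .25) = .866. Approximate 95% half-widths for a difference in slopes, to be read against a common slope of .5:
- Trained 60 v control 30: 1.96 x .866 x sqrt(1/60 + 1/30) = .38.
- Affective 30 v neutral 30: 1.96 x .866 x sqrt(2/30) = .44.
- The same two arms by sex, four cells of 15: 1.96 x .866 x sqrt(4/15) = .88.

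**The case against.** The strongest reply is that the plan never schedules a correlation of a baseline score with its own gain. That is so. The reference to correlational methods belongs to the secondary aims, not to E4, and the exploratory variable lists do not name baseline cognitive score. The Data Analysis Strategy says Aims 1-3 are handled in the transfer and training analyses, which are mixed models and linear contrasts. But those models, as described, contain neither baseline performance as a predictor nor relapse, so E4 is still without a model.

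A reader might infer that E4 will produce a spurious sex difference. The documents do not support that. E4 compares a relationship between the sexes, and step 4 shows that the artefact cancels when reliability and SD ratio are alike, and inflates error only modestly when they are not.

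A reader might also apply -.50 to every use of gains. That goes too far. E3 and the separate training-effects paragraph suggest that training gains may mean gains on the n-back and attend/ignore tasks, which are not in the baseline assessment. Step 3 then applies, not step 2.

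Finally, the work is a pilot, these analyses are labelled exploratory, and a retested control group exists that could expose the artefact. All true. But the plan does not say the control group will be used in this way, and an exploratory label does not make a correlation with gain measure response to training.

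**Conclusion.** The concern holds for the search for correlates and subgroups of response, and for E4 as a question left without a model. Correlating characteristics with pre-post gain cannot separate response to training from regression to the mean, practice or recovery. Where the characteristic is the baseline score on the same test, the null correlation is -.50 under rho = .5 and equal SDs, -.59 to -.32 over assumed rho of .3 to .8, and it would usually reach nominal significance at 30 to 60 participants. For other characteristics the size is unknown and may be zero.

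It is not shown that E4's sex comparison is biased, or that the investigators will misread these results. The point does not concern the main comparison of conditions. It is worth correcting before analysis because the subgroup findings are meant to shape the next study.

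**What to change.** Amend the Data Analysis Strategy as follows.

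- For each moderator, model retest score on baseline score, condition, sex, the moderator and moderator x condition, in all participants. Where the question is baseline performance, baseline score is itself the moderator.
- Define response to training as the moderator x condition term, either against control or between the neutral and affective arms. Only the second contrast is randomised: controls are recruited before and after the training groups, and this should be stated with any result against them.
- State what training gains means in E4 and which baseline measure it is set against. Controls have no training-task data, so on that reading only the two trained arms can be compared.
- Test E4 by a sex x slope term, not by comparing two correlations, which also depend on each sex's score spread. A sex x baseline slope can still reflect a sex difference in reliability. The sex x baseline x condition term does not, provided reliability is alike across arms.
- State that within-arm correlations of baseline with gain will not be interpreted as response.

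The cost is wording only; all the data are already planned. The drawback is precision. The half-widths in step 6 are nearly as large as the common slope, or larger once sex is added, and they allow for no dropout. For links with relapse, the plan expects only about 60% to complete all interviews (.6 x 90 = 54). These terms should therefore be reported as estimates with confidence intervals and labelled exploratory.

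### The exploratory aim asks who responds to training but names only correlation, which cannot separate response to training from prognosis; no characteristic-by-condition term is stated except for sex

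*Combined protocol and SAP*

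**What the plan says.** Section 5 (Secondary/Exploratory Aims) is interested in characteristics "that may impact the efficacy of training interventions, e.g., pre-treatment levels of functional adaptation, mood/affect during treatment, and comorbid substance use". It then gives the method: "These associations will be examined in exploratory analyses relying on correlational methods and will inform future projects".

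In section 6, the Data Analysis Strategy has two parts for this aim. The first is to "examine associations between/among measures of functional adaptation, mood/affect, transfer gains and post-treatment substance use". The second is to "explore potential subgroups/subtypes that vary in response to training and/or post-treatment outcomes"; no method is named for it. The Overall Summary in section 4 gives the purpose: the data should "identify potential subgroups (beyond sex) varying in response" and guide an R01 application.

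The opening of section 6 explains the third arm: "The control Ss will meet identical selection criteria but complete only baseline and retesting, controlling for abstinence-related improvement". That arm enters the main transfer analysis: "GLMM analyses will be employed to examine effects of training condition, sex, and their interaction on transfer task performance". Sex is the only participant characteristic for which an interaction with condition is stated.

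On allocation, section 6 randomises neutral versus affective training within sex. Controls are enrolled partly before and partly after the training groups, and the Data and Safety Monitoring Plan confirms that assignment to control depends on the phase of the project.

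**The concern.** Whether a characteristic changes the efficacy of training is a question of effect modification: does the difference between conditions depend on that characteristic? A correlation between the characteristic and gain answers another question, namely who improves.

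Gain from baseline to retest has at least three components: benefit from training, recovery with abstinence, and practice on the tests. The plan expects the second. Section 4 says that recovery of function can be anticipated and is uneven across domains, and section 6 keeps a control arm because of it. A characteristic that predicts recovery or practice will correlate with gain even if training helps everyone equally, or nobody.

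For sex the plan deals with this through the condition-by-sex interaction. For mood, adaptation and comorbid use it states no such safeguard. At stake is how candidate subgroups are chosen for the follow-on application: a prognostic marker could be carried forward as a marker of response, and a true modifier could be missed.

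**Working it through.** **Plan's own figure.** No power or precision is given for this aim. The nearest figure is .96 for sex by condition (f = .25, rho = .5, alpha = .05). It reproduces as a six-group-by-time test: noncentrality = f² × N × m / (1 − rho) = .0625 × 90 × 2 / .5 = 22.5 on (5, 84) df, power .962. The 2-df sex-by-condition-by-time test on the same inputs gives .991. Neither covers a characteristic other than sex.

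**Inputs.**
- From the Abstract and Table 1: 60 trained (30 neutral, 30 affective) and 30 controls.
- From the Data Analysis Strategy: a dropout scenario of 10 per condition, leaving 40 trained and 20 controls.
- From Follow-up: about 60% complete all interviews, which is 36 trained and 18 controls if equal across arms.
- Assumed, because the documents give no value: the characteristic correlates r = .3 with gain (range .2 to .4), identically in every arm, so there is no effect modification.

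**Step 1: correlation in the trained participants.** By Fisher z, power ≈ Φ(atanh(r) × √(n − 3) − 1.96), with √57 = 7.55 at n = 60:
- r = .2: Φ(.203 × 7.55 − 1.96) = .33
- r = .3: Φ(.310 × 7.55 − 1.96) = .65
- r = .4: Φ(.424 × 7.55 − 1.96) = .89

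Simulation gives .336, .652 and .897. With 40 trained completers it gives .235, .476 and .741.

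**Step 2: correlation pooled over all 90.** In simulation, with the same mean training gain (.5 SD) for everyone, the rates for r = .2, .3 and .4 are 45%, 80% and 97%. Adding controls without a condition-by-characteristic term makes the problem worse.

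**Step 3: characteristic-by-condition interaction, trained versus control.** Under the same assumption it is significant in about 5% of trials (.049 to .055 at 60 versus 30; .0505 at 40 versus 20).

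**Step 4: the opposite error.** Let the slope be −.3 in controls and 0 in trained participants, a true modifier. The trained-only correlation is significant in 5% of trials and the interaction in 27%.

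**Step 5: what the interaction can deliver.** With residual SD 1 and a standardised characteristic, the standard error of the slope difference is about √(1/60 + 1/30) = .224, so the 95% half-width is 1.96 × .224 = .44 SD. For affective versus neutral it is 1.96 × √(1/30 + 1/30) = .51 SD. Simulated power at 60 versus 30 is about 25% for a slope difference of .3 SD and 58% for .5; at 36 versus 18 it is 16% and 38%.

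**The case against.** The case on the other side is substantial.

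- A reader might infer that the control arm is left out. The documents do not support that. Controls are in the transfer GLMM, nothing confines the exploratory work to trained participants, and the subgroup search names no method and excludes none. What stands is that the control arm is not named for this aim, while section 5 does name correlation.
- The aim can be read as associational, since it speaks of relationships and of characteristics that may matter. For that reading correlation is adequate. It does not cover the wording about subgroups that vary in response to training.
- The 65% is simply the power of a correlation test under an assumed r. It becomes a false lead only if the association is then read as response to training. That is accepted; the figure shows how easily such a reading would arise, not how often it will.
- A reader might infer that the subgroups found would mostly be people with a better natural course. The calculation sets true modification to zero, so it cannot support a statement about proportions.
- The control arm does not fully solve the problem. It is not randomised, so an interaction with it rests on comparability over time. Controls have no training-task gains. Mood during treatment may be measured after training starts, because BDI-II and AI are repeated at retest. These points limit the remedy but do not make correlation answer the question.
- Interaction power is low. That argues for estimates with intervals, not for a method aimed at a different quantity.

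**Conclusion.** The concern holds in this form: the aim includes a question about response to training, the only method named for it is correlation, and no characteristic-by-condition term is stated except for sex. A purely prognostic characteristic would be significant in about 65% of trained-only correlations at n = 60 (34% to 90% for r from .2 to .4), against 5% for the interaction. These figures rest on an assumed r that is equal in all arms.

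The exploratory label excuses imprecision and multiplicity, but not a mismatch between question and method. Since this is a secondary aim in a pilot and no confirmatory claim depends on it, the weight is modest: it should be corrected because correction is cheap.

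**What to change.** In section 5 (Secondary/Exploratory Aims) and in the Data Analysis Strategy, state the following.

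- Candidate characteristics measured before training (for example BDI-II and AI at screening or baseline, and comorbid substance use) are examined as characteristic-by-condition terms in the planned GLMM for transfer outcomes, with time where the model uses repeated scores.
- Two contrasts are reported: affective versus neutral, which is randomised, and trained versus control, labelled non-randomised and enrolled by project phase.
- The slope in each arm is shown with its confidence interval, and interactions are presented as exploratory estimates, not tests.
- Plain correlations, and any analysis of mood measured after training starts, are described as prognostic or descriptive only.

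Before this is applied to post-treatment outcomes, reconcile the opening of section 6, where controls complete only baseline and retesting, with the Data and Safety Monitoring Plan, where all participants are contacted after the intervention.

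The cost is SAP wording; no new data, visits or participants are needed. The downside is imprecision, with half-widths of about .44 to .51 SD at full enrolment and wider after dropout.

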Cognitive Training. Training will be conducted over up to three weeks at the treatment facility. Training will involve performance-based progression, an important characteristic of effective training [56; 60]. We will use the dual n-back as reported by Schwiezer et al [60] and a modification of a directed attend/ignore tasks used in our prior work [e.g., 100]. Ss will be instructed to complete twelve training sessions over three weeks (4/week), each lasting 45-50 min. Ss completing 2 or fewer sessions in the first week or withdrawing during this time will be discontinued from study and replaced. Drop-outs after the 1st week of training will not be replaced. The number of sessions completed/week will inform future study development and will be used as a descriptive variable and in covariate analyses, as appropriate. Given study objectives, compensation will be provided on a daily basis (\$15/session), with a bonus for completing at least nine sessions (\$20 for sessions 9-12). Study staff will be present for all training to ensure S identification, assist with software issues, provide compensation, and ensure data integrity. Throughout training, one group will train with versions of the tasks using emotionally-laden stimuli (Affective Training Group); one group will train using emotionallyneutral versions of the tasks (Neutral Training Group). To parallel Schwiezer's work and given alcoholics' deficits in the processing of negative emotion [65; 71; 101], affective stimuli will reflect negative states. All face models will be presented an equal number of times across affect categories (i.e., no individual face actor will appear more often as "angry" than "fearful").

Training sessions. Although treatment facilities are smoke-free, several provide areas for smoke breaks. Therefore, Ss will be informed during consenting and reminded prior to the training session that smoke breaks will not be allowed during training and advised to have their last smoke within an hour before each training session. At the initiation of each session, Ss will provide information regarding time/quantity of last nicotine use. These data will be used in descriptive and covariate analyses, as appropriate. To provide pilot data regarding training acceptability and presuming that acceptability may vary with progress, after each

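### Affective vs neutral training is to be compared on change scores; adjusting for baseline Stroop would usually be more precise (about 24% less variance on the plan's own correlation)

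*Combined protocol and SAP*

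**What the plan says.** Section 6 (Research Plan) sets the design: "The primary design is a 2 (Sex) by 3 (Training Condition: Neutral, Affective, Control) by 2 (Time: Baseline, Post-training) mixed design". It then defines the outcome: "The primary dependent variables are differences between pre- and post-intervention performance on the two Stroop tasks as a function of training condition", with sex and the sex-by-condition interaction also named.

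On allocation, the same section states: "Assignment to neutral vs. affective training group will be randomized within sex". Controls are not randomised alongside the trained groups; about half are enrolled before the training groups and half after.

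Two hypotheses in section 5 (Aims) rest on the randomised comparison. H2 reads "Training with affective stimuli as opposed to neutral stimuli will differentially benefit performance on transfer tasks engaging affective stimuli" and H4 reads "Training with affective stimuli may differentially benefit women as compared to men".

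The Data Analysis Strategy says: "GLMM analyses will be employed to examine effects of training condition, sex, and their interaction on transfer task performance". It does not say how baseline enters that model. The only covariates called key appear in the secondary aims, as an open list: "beyond those treated as key covariates, e.g., age, education, alcohol use history". Session counts, nicotine use and screening data may also serve as covariates where appropriate. E4 mentions baseline performance, but as a relationship to study and not as an adjustment.

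**The concern.** When two arms are randomised, a difference between them at baseline is chance. A change score subtracts the whole baseline value. Regression on baseline subtracts only the part that predicts the post-training score. The second approach has the smaller residual variance unless the slope of post on baseline is 1.

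The planned mixed model does not settle the matter. With free baseline means and complete data, its condition-by-time contrast is the change-score contrast.

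What is at stake is precision, not bias. H2 rests on 30 per arm and H4 on 15 per cell. Under the dropout in the power paragraph these become 20 and, if losses are equal in men and women, 10. The estimates are meant to guide a larger application, so interval width matters.

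**Working it through.** **Inputs from the documents.** 60 participants randomised 1:1 within sex, four cells of 15 (section 6, Table 1). Planning correlation rho = .5, moderate effect f = .25, alpha .05, interaction power .96, and a dropout scenario of 10 per condition (power paragraph). The post/pre SD ratio k is not given, so k = .8, 1 and 1.25 are assumed, as is any rho other than .5.

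**The plan's own figure.** With two repeated measures, lambda = N × f² × 2/(1 − rho) = 90 × .0625 × 2/.5 = 22.5. With 5 and 84 df, power is .962 against the stated .96. The factor (1 − rho) is the change-score error term, so rho = .5 is the pre-post correlation.

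**Variance of the two analyses**, with SD the baseline SD:

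- Change: (1 + k² − 2·rho·k)·SD². At rho = .5, k = 1 this is 1.00 SD².
- Baseline-adjusted: k²(1 − rho²)·SD². At rho = .5, k = 1 this is .75 SD².
- Cost of estimating the slope: multiply the adjusted variance by 1 + 1/(N − 6), which is 1.0185 at N = 60 and 1.0294 at N = 40.

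At rho = .5, k = 1, N = 60, the net ratio is .75 × 1.0185 = .764, or about 24% less variance. Net ratios, adjusted over change:

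| N | k | rho .3 | rho .5 | rho .7 | rho .8 |
|---|---|---|---|---|---|
| 60 | .8 | .511 | .582 | .639 | .652 |
| 60 | 1 | .662 | .764 | .866 | .917 |
| 60 | 1.25 | .799 | .909 | .999 | 1.019 |
| 40 | 1 | .669 | .772 | .875 | .926 |
| 40 | 1.25 | .808 | .919 | 1.010 | 1.029 |

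Before the slope cost, the gain is zero exactly when rho × k = 1.

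**95% interval half-widths**, rho = .5, k = 1, in baseline SDs. With v the variance above, these are t(.975) × √(4v/N) for H2 and t(.975) × √(16v/N) for H4, with N − 4 error df for change and N − 5 for adjusted.

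| | Change | Adjusted |
|---|---|---|
| H2, N = 60 | .52 | .45 |
| H4, N = 60 | 1.03 | .90 |
| H2, N = 40 | .64 | .56 |
| H4, N = 40 | 1.28 | 1.13 |

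At k = 1.25, N = 60, the H2 half-width goes from .59 to .57 (rho .5), stays at .47 (rho .7), and goes from .388 to .392 (rho .8).

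**Power on the plan's effect size.** For the two randomised arms at N = 60, lambda = 60 × .0625 × 2/.5 = 15. Setting 15 = d² × 60/(4 × 2 × .5) gives d = 1.0 SD for H2. The matching difference of differences for H4 is 2.0 SD. Power by noncentral F with 1 df is .968 for change and .992 for adjusted. At N = 40, lambda = 10 and power is .868 and .938.

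**Power for smaller effects, which are assumptions** (H2, N = 60, rho = .5, k = 1): .8 SD, .86 to .94; .5 SD, .48 to .59; .3 SD, .21 to .26.

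**Simulation** (20,000 runs per setting) agrees. At 15 per cell, rho = .5, k = 1, the variance ratios are .763 (H2) and .767 (H4). Power is .969 to .991 (H2) and .968 to .991 (H4); at 10 per cell it is .870 to .937 and .872 to .939. Type I error is .049 to .051 for both methods.

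**The case against.** Nothing in the plan is wrong in the sense of biased. The covariate list is open, and the model description leaves room for a form that constrains baseline means and would recover most of the gain. The power section is not clear proof of intent either. The .96 needs a 5-df test over six groups; a 2-df test on the same inputs gives .991. The .78 and .98 figures reproduce with the (1 + rho) error term, which averages over time. The 1.0 and 2.0 SD effects are derived here and the plan does not state them. The size of the gain depends on two unknowns, and this is a pilot.

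Most of this is fair, and it limits the claim to lost precision of uncertain size. It does not remove the point. The stated outcome is the change score, and no passage supplies an adjustment, so following the text gives the less precise estimate in most settings shown.

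A smaller objection is that a six-cell change analysis has 84 error df, not 56. That moves the H2 half-width only from .517 to .513. The remaining objection, that H1 and H2/H4 would come from different models, is a real cost.

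**Conclusion.** The concern holds. For affective vs neutral on a given Stroop measure, the planned change score is valid but usually less precise than baseline adjustment: about 24% less variance at rho = .5 with equal SDs, and 49% less to 2% more over the range shown at N = 60. At the plan's effect size the power gain is small at full enrolment and larger after dropout. The main return is narrower intervals and more power if true effects are smaller than planned. Very small effects stay out of reach.

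Limits:

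- The figures apply to outcomes fitted with a linear model, such as reaction time or efficiency, and not to accuracy under a non-identity link.
- They do not cover a reading of H2 as condition by task (emotional vs standard Stroop), which needs cross-task correlations that the documents do not give.
- They do not extend to comparisons with controls or between the sexes, which are not randomised.
- Adjustment does not repair the post-assignment rule "Ss completing 2 or fewer sessions in the first week or withdrawing during this time will be discontinued from study and replaced".

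This is an improvement that should be made; no stated figure is in error.

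**What to change.** Prespecify for H2 and H4: *Among participants randomised to affective or neutral training, the post-training score of each Stroop measure will be modelled on condition, sex and condition × sex, with the baseline score of the same measure as covariate.*

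An alternative within the planned framework is a mixed model that constrains baseline means to be equal across the two randomised arms within each sex. With complete data it is nearly equivalent, and it also keeps participants who have a baseline score only. State the link used for accuracy. Keep the change analysis for trained vs control and men vs women, where true baseline differences are possible.

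The cost is one degree of freedom per outcome and a second model for each Stroop measure. If the correlation is high and SDs grow after training, there is no gain or a loss of about 2 to 3%. No new data or visits are needed.
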